**Appendix 3: Schedule of Pharmacokinetic, Immunogenicity, and Biomarker Samples**

Visit	Timepoint	Sample Type
Cycle 1, Day 3	Arms A and C: 40–48 hr after end of C1D1 infusion Arm B: 20–24 hr after end of C1D2 infusion	Peripheral biomarkers (plasma and serum)
		Flow cytometry and PBMC isolation (whole blood)
		PK (serum)
Cycle 1, Day 8	Pre-infusion a	Peripheral biomarkers (plasma and serum)
		Flow cytometry and PBMC isolation (whole blood)
		PK (serum)
		Exploratory PK (serum)
	End of infusion (+30 min)	Peripheral biomarkers (plasma and serum)
		PK (serum)
	2 hr after end of C1D8 infusion (±30 min)	Peripheral biomarkers (plasma and serum)
		PK (serum)
Cycle 1, Day 9	20–24 hr after end of C1D8 infusion	Peripheral biomarkers (plasma and serum)
		Flow cytometry and PBMC isolation (whole blood)
		PK (serum)
Cycle 2, Day 1	Pre-infusion a	Peripheral biomarkers (plasma and serum)
		Flow cytometry and PBMC isolation (whole blood)
		PK (serum)
		Exploratory PK (serum)
		ADA (serum)
	End of infusion (+30 min)	Peripheral biomarkers (plasma and serum)
PK (serum)		
Cycle 2, Day 8	Pre-infusion a	Peripheral biomarkers (plasma and serum)
		PK (serum)
	End of infusion (+30 min)	Peripheral biomarkers (plasma and serum)
		PK (serum)

**Appendix 3: Schedule of Pharmacokinetic, Immunogenicity, and Biomarker Samples**

Visit	Timepoint	Sample Type
Cycle 3, Day 1	Pre-infusion a	Peripheral biomarkers (plasma and serum)
		Flow cytometry and PBMC isolation (whole blood)
		PK (serum)
		Exploratory PK (serum)
		ADA (serum)
	End of infusion (+ 30 min)	Peripheral biomarkers (plasma and serum)
		PK (serum)
Cycle 3, Day 8	Pre-infusion a	Peripheral biomarkers (plasma and serum)
		PK (serum)
	End of infusion (+ 30 min)	Peripheral biomarkers (plasma and serum)
		PK (serum)
Cycles 4, 6, and 8, Day 1	Pre-infusion	Peripheral biomarkers (plasma and serum)
		Cell-free DNA (whole blood) c
		ADA (serum)
		PK (serum)
Cycle 14, Day 1, and Day 1 every six cycles thereafter (i.e., Cycles 20, 26, 32, etc.)	Pre-infusion	Peripheral biomarkers (plasma and serum)
		PK (serum)
		ADA (serum)
Day 1 of any intrapatient dose escalation	Pre-infusion a	Peripheral biomarkers (plasma and serum)
		PK (serum)
		Exploratory PK (serum)
		ADA (serum)
	End of infusion (+ 30 min)	Peripheral biomarkers (plasma and serum)
		PK (serum)
	2 hr after end of infusion (± 30 min)	Peripheral biomarkers (plasma and serum)
		PK (serum)

### Appendix 3: Schedule of Pharmacokinetic, Immunogenicity, and Biomarker Samples

---

Visit	Timepoint	Sample Type
End of treatment visit	Any time	Flow cytometry and PBMC isolation (whole blood)
		Cell-free DNA (whole blood)
		Peripheral biomarkers (plasma and serum)
		PK (serum)
		ADA (serum)

ADA=anti-drug antibody; C=cycle; D=day; PBMC=peripheral blood mononuclear cell; PK=pharmacokinetic; WGS=whole genome sequencing.

Note: Study assessments may be delayed or moved ahead of the window to accommodate holidays, vacations, and unforeseen delays.

- a Pre-infusion collection should be taken within 2 hours prior to infusion.
- b Whole blood sample for WGS should be collected on Cycle 1, Day 1; however, it may be collected at any time during the study after Cycle 1, Day 1.
- c Cell-free DNA will only be collected on Cycle 4, Day 1.

## Appendix 4

### Guidelines for the Determination of Prior Lines of Therapy

Source: Rajkumar et al. 2014.

#### **LINE OF THERAPY**

A line of therapy is defined as  $\geq 1$  complete cycle of a single agent, combination regimen of several drugs, or a planned sequential therapy of various regimens (e.g., induction with a multi-agent regimen followed by autologous stem cell transplantation, consolidation and lenalidomide maintenance is considered one line).

#### **NEW LINE OF THERAPY**

A treatment is considered a new line of therapy if any one of the following three conditions is met:

Definition of a New Line of Therapy	Comments
Discontinuation of one treatment regimen and start of another	A regimen is considered to have been discontinued if all drugs in that given regimen have been stopped.  The reasons for discontinuation, addition, substitution, or SCT do not influence how lines are counted.
Unplanned addition or substitution of one or more drugs in a regimen	Unplanned addition of a new drug or switching to a different drug (or combination of drugs) due to any reason is considered a new line of therapy.
In patients undergoing $> 1$ SCT, each SCT is considered a new line of therapy	Except in the cases of a planned tandem SCT performed $< 6$ months from the first SCT, each additional SCT is considered a new line of therapy.

SCT = stem cell transplant.

#### **INTERRUPTIONS AND DOSE MODIFICATIONS**

If a regimen is interrupted or discontinued for any reason and the same drug or combination is restarted without any intervening regimen, then it should be counted as a single line.

If a regimen is interrupted or discontinued for any reason and then restarted at a later timepoint, but one or more other regimens were administered in between, or the regimen is modified through the addition of one or more agents, then it should be counted as two lines.

## Appendix 5 International Myeloma Working Group Uniform Response Criteria (2016)

Adapted from Durie et al. 2015 and Kumar et al. 2016.

### **COMPLETE RESPONSE AND OTHER RESPONSE CATEGORIES**

Response Subcategory	Response Criteria
All response categories require two consecutive assessments made any time before starting any new therapy.	
sCR	CR as defined below, plus: Normal FLC ratio and absence of clonal cells in BM by immunohistochemistry (kappa/lamda ratio $\leq$ 4:1 or $\geq$ 1:2 for kappa and lambda patients, respectively after counting $\geq$ 100 plasma cells) a
CR	No evidence of initial monoclonal protein isotype(s) on immunofixation of the serum and urine, b disappearance of any soft tissue plasmacytomas, and $\leq$ 5% plasma cells in BM
VGPR	Serum and urine M-protein detectable by immunofixation but not on electrophoresis; or $\geq$ 90% reduction in serum M-protein plus urine M-protein level < 100 mg/24 hr
PR	$\geq$ 50% reduction of serum M-protein and reduction in 24-hour urine M-protein by $\geq$ 90% or to < 200 mg/24 hr 
 
• If the serum and urine M-protein are unmeasurable, a <math>\geq</math> 50% decrease in the difference between involved and uninvolved FLC levels is required in place of the M-protein criteria.
 
• If serum and urine M-protein are unmeasurable and serum FLC assay is also unmeasurable, <math>\geq</math> 50% reduction in plasma cells is required in place of M-protein, provided baseline BM plasma cell percentage was <math>\geq</math> 30%
 
• In addition to the above listed criteria, if present at baseline, a <math>\geq</math> 50% reduction in the size (SPD) c of soft tissue plasmacytomas is also required.
 

MR	$\geq$ 25% but $\leq$ 49% reductions of serum M-protein and reduction in 24-hour urine M-protein by 50%–89% 
 
• In addition to the above criteria, if present at baseline, 25%–49% reduction in the size (SPD) c of soft tissue plasmacytomas is also required.
 

SD	Not meeting criteria for MR, CR, VGPR, PR, or PD

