#### 4.1.1 **Inclusion Criteria**

Patients must meet the following criteria for study entry:

- Signed Informed Consent Form
- Age  $\geq 18$  years at time of signing Informed Consent Form
- Ability to comply with the study protocol, in the investigator's judgment
- Eastern Cooperative Oncology Group (ECOG) Performance Status of 0 or 1  
ECOG Performance Status of 2 due to MM may be eligible after discussion with the Medical Monitor.
- Life expectancy of at least 12 weeks
- Patients must have R/R MM for which no established therapy for MM is appropriate and available or be intolerant to those established therapies
- Agreement to provide bone marrow biopsy and aspirate samples as detailed in [Appendix 1](#)
- Adverse events from prior anti-cancer therapy resolved to Grade  $\leq 1$ , with the following exceptions:
  - Any grade alopecia
  - Peripheral sensory or motor neuropathy that has resolved to Grade  $\leq 2$
- Measurable disease, defined as at least one of the following:
  - Serum monoclonal protein (M-protein)  $\geq 0.5$  g/dL ( $\geq 5$  g/L)
  - Urine M-protein  $\geq 200$  mg/24 hr
  - Serum free light chain (SFLC) assay: Involved SFLC  $\geq 10$  mg/dL ( $\geq 100$  mg/L) and an abnormal SFLC ratio ( $<0.26$  or  $>1.65$ )
- Laboratory values as follows:
  - Hepatic function:
    - AST and ALT  $\leq 3 \times$  ULN
    - Total bilirubin  $\leq 1.5 \times$  ULN  
Patients with a documented history of Gilbert syndrome and in whom total bilirubin elevations are accompanied by elevated indirect bilirubin are eligible.
  - Hematologic function:
    - Platelet count  $\geq 50,000/\text{mm}^3$  without transfusion within 7 days of assessment
    - ANC  $\geq 1000/\text{mm}^3$
    - Total hemoglobin  $\geq 8$  g/dL without transfusion within 14 days of assessment

Patients who do not meet criteria for hematologic function because of MM related cytopenias (e.g., due to extensive marrow involvement by MM) may be enrolled into the study after discussion with the Medical Monitor.

- Creatinine clearance (CrCl)  $\geq 30$  mL/min (either calculated using a modified Cockcroft-Gault calculation or per 24-hour urine collection; inulin or radionuclide-based methods may be used after discussion with Medical Monitor)
- Serum calcium (corrected for albumin) level  $\leq 11.5$  mg/dL (2.9 mmol/L)

Treatment of hypercalcemia is allowed and patient may enroll if hypercalcemia returns to normal with standard treatment.

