## **6.8 INTERIM ANALYSES**

Continuous safety monitoring and interim analyses will be performed for the expansion portion of the study to guide potential early stopping of enrollment in the event of unacceptable toxicity or a lower than expected response rate.

A Bayesian posterior probability approach (Thall and Simon 1994) with a uniform prior will be used to evaluate toxicity, including the rate of DLTs. If at any time in the expansion cohort, the number of observed DLTs indicates that there is an approximately 80% chance that the true DLT rate is  $\geq 20\%$  (e.g., DLTs observed in 2/5, 3/10, 4/15, 5/20 patients), accrual to the cohort may be paused and the ISC will meet to determine whether further enrollment in the cohort should be halted taking into account feedback from study investigators.

A similar approach will be used to assess the response rate. Specifically, after approximately 15 patients in the expansion cohort have completed their first tumor assessment, an interim analysis will be conducted to inform potential early stopping of enrollment if observed response rates are lower than expected. Using the Bayesian posterior probability approach with a uniform prior, the cohort may be stopped if the objective response rate is less or equal to 25% with a probability greater or equal to 60%. This would be the case for example if 2 or fewer out of the first 15 patients have an objective response. At each interim analysis, the ISC will review the response data and decide whether to recommend an early decision to stop enrollment in the subgroup due to futility. Additional futility analyses may be conducted in periodic review of efficacy data. In all cases, decisions to stop enrollment into the expansion cohort will be made in consultation with study investigators.

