**Appendix 5: International Myeloma Working Group Uniform Response Criteria (2016)**

**DISEASE PROGRESSION AND RELAPSE**

Relapse Subcategory	Relapse Criteria
PD d, e	
Any one or more of the following criteria:
 
 
• Increase of <math>\geq 25\%</math> from lowest response value in one or more of the following:               
 
• Serum M-protein (absolute increase must be <math>\geq 0.5</math> g/dL)
 
• Serum M-protein increase <math>\geq 1</math> g/dL, if the lowest M component was <math>\geq 5</math> g/dL
 
• Urine M-protein (absolute increase must be <math>\geq 200</math> mg/24 hr)
 
 
 
• In patients without measurable serum and urine M-protein levels: the difference between involved and uninvolved FLC levels (absolute increase must be <math>> 10</math> mg/dL)
 
• In patients without measurable serum and urine M-protein levels and without measurable disease by FLC: BM plasma cell percentage irrespective of baseline status (absolute % must be <math>\geq 10\%</math>)b
 
• Appearance of new lesion(s), <math>\geq 50\%</math> increase from nadir in SPD of <math>> 1</math> lesion, or <math>\geq 50\%</math> increase in the longest diameter of a previous lesion <math>> 1</math> cm in short axis
 
• <math>\geq 50\%</math> increase in circulating plasma cells (minimum 200 cells per microliter) if this is the only measure of disease
 

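### As printed, the first VGPR alternative in Appendix 5 can be met at baseline by some patients eligible on serum free light chains alone, so unchanged disease can count in the ORR

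*Combined protocol and SAP*

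**What the plan says.** Section 4.1.1 of the protocol requires "Measurable disease, defined as at least one of the following", and one of the three routes is "Serum free light chain (SFLC) assay: Involved SFLC" at or above 10 mg/dL with an abnormal ratio. A patient can therefore enter with serum M-protein below 0.5 g/dL and urine M-protein below 200 mg/24 hr. The plan expects such patients: Section 4.5.6 and Appendix 1 make separate provision for light-chain-only disease when historical values are collected.

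Appendix 5 treats free light chains as follows:

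- **PR:** if serum and urine M-protein are unmeasurable, a 50% or greater "decrease in the difference between involved and uninvolved FLC levels is required in place of the M-protein criteria".
- **VGPR:** first alternative, "Serum and urine M-protein detectable by immunofixation but not on electrophoresis"; second alternative, a fall of at least 90% in serum M-protein with urine M-protein below 100 mg/24 hr. Neither carries an FLC condition.
- **CR:** "No evidence of initial monoclonal protein isotype(s) on immunofixation of the serum and urine", no remaining soft tissue plasmacytoma, and marrow plasma cells of 5% or less. There is no FLC condition.
- **sCR:** CR plus "Normal FLC ratio and absence of clonal cells in BM by immunohistochemistry".
- **PD:** a separate rule, "In patients without measurable serum and urine M-protein levels: the difference between involved and uninvolved FLC levels", with a minimum absolute increase.

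Every response category needs two consecutive assessments. Sections 2.3 and 6.6 count sCR, CR, VGPR and PR as objective response, as determined by the investigator. Section 6.8 uses the ORR for a futility look after about 15 expansion patients.

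**The concern.** The first VGPR alternative describes what the laboratory shows on a given day. That works for a patient who began with a visible M-protein, because losing it on electrophoresis is itself a change. It does not work for a patient who never had one. An SFLC-only patient whose serum and urine are positive on immunofixation and negative on electrophoresis at Cycle 1, Day 1 meets the wording before any drug effect and goes on meeting it while the disease is unchanged.

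Such a patient would be counted in the ORR, and Section 6.6 would start a duration of response at that assessment. The ORR is the main activity endpoint, it feeds the futility look in Section 6.8, and clinical activity is among the data that inform the RP2D. The expansion cohort has about 30 patients and the futility boundary turns on one patient, so a single misclassification can be visible.

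**Working it through.** **1. Does anything else in the documents close the gap?**

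- *Two-assessment rule (Appendix 5).* An unchanged baseline state passes it twice.
- *Confirmatory tests (Section 4.5.6).* VGPR calls for 24-hour urine electrophoresis and immunofixation, plus imaging if there was extramedullary disease. No SFLC value is set. For CR and sCR an SFLC sample must be obtained, but no value is attached to CR.
- *Hierarchy.* No text says that VGPR also requires PR. Stable disease is a residual category that excludes anyone meeting VGPR, so as printed this patient is not stable disease.
- *Footnotes to Appendix 5.* The CR footnote concerns the isotype on immunofixation, not the FLC level.

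Nothing closes it.

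**2. The plan's own figures.**

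- Section 6.1, 30 patients, 20% observed: 0.20 ± 1.645 × √(0.2 × 0.8/30) = 8.0% to 32.0%. This matches the printed 90% interval of (8%, 32%).
- Section 6.8, uniform prior, x responses in 15, posterior Beta(1 + x, 16 − x): P(ORR ≤ 25%) = 0.803 at x = 2 and 0.595 at x = 3. With a 60% cutoff the boundary is 2 or fewer of 15, as printed.

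**3. How many patients could be affected.** The documents give neither share, so both are assumptions.

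- f = share of patients measurable by SFLC only: 5–20%.
- q = share of those who are immunofixation-positive and electrophoresis-negative in both serum and urine at baseline: 10–50%.
- f × q = 0.05 × 0.10 = 0.5% up to 0.20 × 0.50 = 10%.
- Of 30 patients: 30 × 0.005 = 0.15 up to 30 × 0.10 = 3.
- Chance of at least one in the first 15: 1 − 0.995^15 = 0.07 up to 1 − 0.90^15 = 0.79.

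**4. Effect on the futility look.** One false responder turns 2/15 into 3/15, and the posterior probability moves from 0.803 to 0.595, just under the cutoff.

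Averaged over how many such patients turn up, let s be the false-response share among true non-responders. I take s = f × q, which assumes that the pattern is unrelated to true response. At a true ORR of 20% the counted rate is 0.20 + 0.80 × s, and the chance of 2 or fewer in 15 is binomial:

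| s | Counted rate | P(≤ 2 of 15) |
|---|---|---|
| 0 | 20.0% | 0.398 |
| 0.5% | 20.4% | 0.383 |
| 5% | 24.0% | 0.264 |
| 10% | 28.0% | 0.165 |

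**5. Effect on the final estimate.** Adding k false responses to 6 true ones, with the same interval formula:

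| k | Observed | 90% interval |
|---|---|---|
| 0 | 6/30 = 20.0% | 8.0% to 32.0% |
| 1 | 7/30 = 23.3% | 10.6% to 36.0% |
| 2 | 8/30 = 26.7% | 13.4% to 39.9% |
| 3 | 9/30 = 30.0% | 16.2% to 43.8% |

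**The case against.** The best case for the plan is that response is an investigator's judgement, SFLC results are available at baseline and every odd cycle, and few investigators would call unchanged disease a very good partial response. In addition, the ORR is a preliminary activity measure, no hypothesis test is planned, and the futility rule is advisory: the cohort may be stopped, after committee review and consultation with investigators. All of that limits the consequences. It does not repair the definition. Section 2.3 ties the endpoint to Appendix 5, and leaving an unwritten stricter rule to about 12 sites invites inconsistent classification.

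Four stronger readings are tempting and should not be drawn.

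- *Every SFLC-only patient becomes a responder.* M-protein below the eligibility threshold may still show on electrophoresis, and the wording, taken literally, needs the pattern in both serum and urine. Nothing in the documents says that the pattern is typical. Only a subset is exposed.
- *CR is equally exposed.* The CR row has the same gap for a patient who is immunofixation-negative at baseline, but CR also needs marrow plasma cells of 5% or less and no plasmacytoma. That route is possible but less likely.
- *Deep FLC responders are lost from the ORR.* An immunofixation-negative patient with a very large FLC fall has no printed route to VGPR, but already meets PR, which counts the same. Only the recorded depth of response changes.
- *Appendix 5 ignores FLC outside PR.* sCR and PD both use it. It is the substitution for M-protein that, among the response categories, stands in the PR row alone.

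**Conclusion.** The point holds on the printed text. A patient eligible on SFLC alone, with immunofixation positive and electrophoresis negative in serum and urine at baseline, meets VGPR without any change and counts in the ORR and the duration of response.

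The size cannot be fixed from the documents. It rests on the two assumed shares above and runs from negligible (0.15 of 30 patients, with hardly any effect on the futility look) to material (3 of 30, with the chance of meeting the futility boundary more than halved at a true ORR of 20%). The non-binding rule and the preliminary status of the endpoint keep this at should-fix. The documents do not support a claim that the ORR or the futility decision will in fact be wrong.

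**What to change.** In Appendix 5, for patients whose serum and urine M-protein are both unmeasurable at baseline:

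1. State that VGPR and CR also require the PR row's FLC criterion, a decrease of at least 50% in the difference between involved and uninvolved FLC.
2. State that the VGPR alternative based on immunofixation and electrophoresis applies only to patients with M-protein measurable at baseline.
3. Fix each patient's measurable parameter at baseline, and use it when deriving ORR and duration of response under Section 6.6 and at the futility look under Section 6.8.

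The sponsor may prefer a deeper FLC threshold for VGPR or CR. That would be a new choice to justify, since Appendix 5 prints no such value for those rows.

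The cost is a few lines of text and a change to the response derivation. SFLC is already drawn at screening, Cycle 1, Day 1 and odd cycles, so no sample or visit is added. The downside is that a few best responses may be downgraded.

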**Appendix 5: International Myeloma Working Group Uniform Response Criteria (2016)**

**DISEASE PROGRESSION AND RELAPSE**

Relapse Subcategory	Relapse Criteria
PD d, e	
Any one or more of the following criteria:
 
 
• Increase of <math>\geq 25\%</math> from lowest response value in one or more of the following:               
 
• Serum M-protein (absolute increase must be <math>\geq 0.5</math> g/dL)
 
• Serum M-protein increase <math>\geq 1</math> g/dL, if the lowest M component was <math>\geq 5</math> g/dL
 
• Urine M-protein (absolute increase must be <math>\geq 200</math> mg/24 hr)
 
 
 
• In patients without measurable serum and urine M-protein levels: the difference between involved and uninvolved FLC levels (absolute increase must be <math>> 10</math> mg/dL)
 
• In patients without measurable serum and urine M-protein levels and without measurable disease by FLC: BM plasma cell percentage irrespective of baseline status (absolute % must be <math>\geq 10\%</math>)b
 
• Appearance of new lesion(s), <math>\geq 50\%</math> increase from nadir in SPD of <math>> 1</math> lesion, or <math>\geq 50\%</math> increase in the longest diameter of a previous lesion <math>> 1</math> cm in short axis
 
• <math>\geq 50\%</math> increase in circulating plasma cells (minimum 200 cells per microliter) if this is the only measure of disease
 

Clinical relapse	
Requires one or more of the following:
 
 
• Direct indications of increasing disease and/or end organ dysfunction (CRAB features)f related to the underlying clonal plasma cell proliferative disorder. It is not used in calculation of time to progression or PFS but is listed here as something that can be reported optionally or for use in clinical practice.
 
• Development of new soft tissue plasmacytomas or bone lesions (osteoporotic fractures do not constitute progression)
 
• Definite increase in the size of existing plasmacytomas or bone lesions. A definite increase is defined as a 50% (and <math>\geq 1</math> cm) increase as measured serially by the sum of the products of the cross-diameters of the measurable lesion.
 
• Hypercalcemia <math>> 11</math> mg/dL (2.65 mmol/L)
 
• Decrease in hemoglobin of <math>\geq 2</math> g/dL (1.25 mmol/L) not related to therapy or other non-myeloma related conditions
 
• Rise in serum creatinine by 2 mg/dL or more (177 <math>\mu</math>mol/L or more) from the start of therapy and attributable to myeloma
 
• Hyperviscosity related to serum paraprotein
 

